10.3 Safety Data

All safety data will be reported. DLT will be examined and the MTD will be determined as previously described. All SAEs will be reported as required.

10.4 Exploratory Aim Analysis

There are a number of patient subgroups that could be of interest and might be expected to respond differently to DDFPe as evaluated by NIHSS scores:

- a. In those early patients who get some successful therapy and get DDFPe early at less than 3 hours from LKWT, the values should drop with the DDFPe and stay down with reperfusion. Late DDFPe uncertain.
- b. In those that get Rx and it fails, scores may perhaps go down with early DDFPe and come back up when it wears off. With late DDFPe little change is expected.
- c. In those that do not get reperfusion therapy and do get DDFPe in the first 3 hours, scores should go down but come back up when it wears off.
- d. In those that do not get reperfusion therapy and get DDFPe late, scores should not change much
- e. In those that get placebo, should see little change, early or late, unless they have successful reperfusion therapy or spontaneous reperfusion.

Fewer than 20% are likely to get IV tPA or IA reperfusion therapy of the total 24 patients; the patient numbers in any of these groups will be quite small, obviating the ability to make formal statistical comparisons or to draw conclusions about the impact of DDFPe therapy on outcome. This is a Phase I safety trial, and not designed to test treatment outcomes. As an exploratory analysis, we will compare the patients without reperfusion therapy, IV or IA, who got early DDFPe under 3 hours from LKWT, to placebo patients of similar characteristics. Due to the small sample sizes and because each of the proposed doses were effective in animal studies, we will ignore dose in this comparison.

We expect that the NIHSS values should drop with DDFPe but come back up after 5 or 6 hours and no change is expected in placebo. We will visually examine plots of the data for consistency with this hypothesis and if the sample sizes are sufficient, we will carry out nonparametric tests comparing the changes as exploratory analyses.

Those patients receiving DDFPe between 3 and 6 hours from LKWT could be another group of great interest, and we will make similar exploratory comparisons of this group with the two just described.

No claims of efficacy will be possible based on these limited data, but they may suggest directions for subsequent study.

11.0 Ethical and Regulatory Requirements

11.1 Trial Registration

The trial will be registered on ClinicalTrials.gov as previously described in Section 4 of the protocol.

11.2 Informed Consent Procedures

This study will be conducted in accordance with all applicable government regulations, research policies and procedures. This protocol and any amendments will be submitted and approved by the local IRB prior to conducting the study.

The formal consent of each subject/LAR, using the IRB-approved consent form, will be obtained before the subject is enrolled into any study procedure. All subjects/LARs for this study will be provided a consent form describing this study and provided sufficient information in language suitable for subjects/LARs to make an informed decision about their participation in this study. The person obtaining consent will thoroughly explain each element of the document and outline the risks and benefits, alternate treatment(s), and requirements of the study. It is anticipated that, due to the nature of the condition under study, some subjects may be unable to provide informed consent. The investigators will follow local IRB policies for obtaining consent from cognitively impaired subjects.

No coercion or undue influence will be used in the consent process. The consent form must be signed by the subject/LAR and the individual obtaining the consent. A copy of the signed consent will be given to the subjects/LARs, and the informed consent process will be documented in each subject's research record.

11.3 Institutional Review Board (IRB)/Independent Ethics Committee (IEC)

This study is to be conducted according to applicable government regulations and Institutional research policies and procedures. The protocol, the consent document, and any amendments will be submitted to a properly constituted independent IRB, in agreement with local legal prescriptions, for formal approval of the study conduct. The decision of the local IRB concerning the conduct of the study will be made in writing to the investigator before commencement of this study.

11.4 Subject Confidentiality

Every effort will be made to assure that data collected from subjects remains confidential. Subjects will be identified by a code. The subject's name and identifying information will be stored in a locked file in the office of the investigator or on a password protected or an encrypted drive in the investigators' personal possession. Data may be shared with NuvOx, the Sponsor (UAMS), the IRB, the FDA, and appropriate compliance and regulatory authorities.

11.5 Protocol Amendments

Any change to the research protocol or consent document must be submitted to and receive approval from the Sponsor, NuVox, and the IRB prior to implementation.

11.6 Study Termination

The study may be terminated at any time by the Sponsor or NuvOx. If the study is terminated, the FDA will be notified.

Title: A phase 1b dose-finding study of DDFPe in acute ischemic stroke
PIs: [name] & [name]
Institution: UAMS
Sponsor: UAMS

In the event that the study is terminated prior to completion, all investigational product will be returned to the pharmacy. The pharmacy will either return the unused product to NuvOx or proceed with destruction of the investigational agent per 21 CFR 312.62.

12.0 Publication Policy

Any manuscripts reporting the results of this clinical trial must be provided to NuvOx by the Principal Investigator for advisory review and comment prior to submission for publication. NuvOx will have 30 days from the date of receipt for review and will also have the right to request that publication be delayed for up to an additional 30 days in order to ensure that confidential and proprietary data, and intellectual property rights, are protected. Copies of meeting abstracts must be provided to NuvOx for courtesy review as soon as possible and at least three (3) days prior to submission. Press releases and other media presentations must also be forwarded to NuvOx prior to release.

In any publication or presentation, individual subjects will not be identified by name or any other means. All data will be published in aggregate form.

Appendix 1: CTCAE 4 Selected Adverse Events

Respiratory, thoracic, and mediastinal disorders					
Adverse Event	Grade				
	1	2	3	4	5
Cough Definition: A disorder characterized by sudden, often repetitive, spasmodic contraction of the thoracic cavity, resulting in violent release of air from the lungs and usually accompanied by a distinctive sound.	Mild symptoms; nonprescription intervention indicated	Moderate symptoms, medical intervention indicated; limiting instrumental ADL	Severe symptoms; limiting self care ADL		
Dyspnea Definition: A disorder characterized by an uncomfortable sensation of difficulty breathing.	Shortness of breath with moderate exertion	Shortness of breath with minimal exertion; limiting instrumental ADL	Shortness of breath at rest; limiting self care ADL	Life-threatening consequences; urgent intervention indicated	Death
Chest Pain Cardiac Definition: A disorder characterized by substernal discomfort due to insufficient myocardial oxygenation.	Mild pain	Moderate pain; limiting instrumental ADL	Pain at rest; limiting self care ADL		
Chest Wall Pain Definition: A disorder characterized by marked discomfort sensation in the pleura.	Mild pain	Moderate pain; limiting instrumental ADL	Severe pain; limiting self care ADL		
Hypoxia Definition: A disorder characterized by a decrease in the level of oxygen in the body.		Decreased oxygen saturation with exercise (e.g., pulse oximeter <88%); intermittent supplemental oxygen	Decreased oxygen saturation at rest (e.g., pulse oximeter <88% or PaO2 <=55 mm Hg	Life-threatening airway compromise; urgent intervention indicated (e.g., tracheotomy or intubation)	Death

Title: A phase 1b dose-finding study of DDFPe in acute ischemic stroke

PIs: [name] & [name]

Institution: UAMS

Sponsor: UAMS

Appendix 2: DDFPe Dosing by Weight

DDFPe dosage volume in cc for **0.05 mL/kg** based on patient body weight in kilograms (kg).

Body Weight (kg)	DDFPe Dose 0.05mL/ kg (mL)	Number of DDFPe 10mL Vials Required	Number of 10mL Syringes	Total Volume to be Prepared (mL)	Volume to be Administered from syringe (mL)
45*	2.2	1	1	10	2.2
46	2.3	1	1	10	2.3
47	2.4	1	1	10	2.4
48	2.4	1	1	10	2.4
49	2.4	1	1	10	2.4
50	2.5	1	1	10	2.5
51	2.6	1	1	10	2.6
52	2.6	1	1	10	2.6
53	2.6	1	1	10	2.6
54	2.7	1	1	10	2.7
55	2.8	1	1	10	2.8
56	2.8	1	1	10	2.8
57	2.8	1	1	10	2.8
58	2.9	1	1	10	2.9
59	3.0	1	1	10	3.0
60	3.0	1	1	10	3.0
61	3.0	1	1	10	3.0
62	3.1	1	1	10	3.1
63	3.2	1	1	10	3.2
64	3.2	1	1	10	3.2
65	3.2	1	1	10	3.2
66	3.3	1	1	10	3.3
67	3.4	1	1	10	3.4
68	3.4	1	1	10	3.4
69	3.4	1	1	10	3.4
70	3.5	1	1	10	3.5
71	3.6	1	1	10	3.6
72	3.6	1	1	10	3.6
73	3.6	1	1	10	3.6
74	3.7	1	1	10	3.7
75	3.8	1	1	10	3.8
76	3.8	1	1	10	3.8
77	3.8	1	1	10	3.8
78	3.9	1	1	10	3.9
79	4.0	1	1	10	4.0
80	4.0	1	1	10	4.0

Title: A phase 1b dose-finding study of DDFPe in acute ischemic stroke

PIs: [name] & [name]

Institution: UAMS

Sponsor: UAMS

Body Weight (kg)	DDFPe Dose 0.05mL/ kg (mL)	Number of DDFPe 10mL Vials Required	Number of 10 mL Syringes	Total Volume to be Prepared (mL)	Volume to be Administered from syringe (mL)
81	4.0	1	1	10	4.0
82	4.1	1	1	10	4.1
83	4.2	1	1	10	4.2
84	4.2	1	1	10	4.2
85	4.2	1	1	10	4.2
86	4.3	1	1	10	4.3
87	4.4	1	1	10	4.4
88	4.4	1	1	10	4.4
89	4.4	1	1	10	4.4
90	4.5	1	1	10	4.5
91	4.6	1	1	10	4.6
92	4.6	1	1	10	4.6
93	4.6	1	1	10	4.6
94	4.7	1	1	10	4.7
95	4.8	1	1	10	4.8
96	4.8	1	1	10	4.8
97	4.8	1	1	10	4.8
98	4.9	1	1	10	4.9
99	5.0	1	1	10	5.0
100**	5.0	1	1	10	5.0

Total DDFPe Dose = 0.05 mL/kg x weight in kg.

*Minimum subject weight = 45 kg.

**Maximum subject weight used for dose calculation = 100 kg. For subjects weighing more than 100 kg, dose will be calculated based on a weight of 100 kg.

Title: A phase 1b dose-finding study of DDFPe in acute ischemic stroke

PIs: [name] & [name]

Institution: UAMS

Sponsor: UAMS

DDFPe dosage volume in cc for **0.10 mL/kg** based on patient body weight in kilograms (kg).

Body Weight (kg)	DDFPe Dose 0.10mL/kg	Number of DDFPe 10mL Vials Required	Number of 10mL Syringes to be Prepared	Total Volume to be Prepared (mL)	Volume to be Administered from 1st syringe (mL)	Volume to be Administered from 2nd Syringe (mL)
45*	4.5	1	1	10	4.5	N/A
46	4.6	1	1	10	4.6	N/A
47	4.7	1	1	10	4.7	N/A
48	4.8	1	1	10	4.8	N/A
49	4.9	1	1	10	4.9	N/A
50	5.0	1	1	10	5.0	N/A
51	5.1	1	1	10	5.1	N/A
52	5.2	1	1	10	5.2	N/A
53	5.3	1	1	10	5.3	N/A
54	5.4	1	1	10	5.4	N/A
55	5.5	1	1	10	5.5	N/A
56	5.6	1	1	10	5.6	N/A
57	5.7	1	1	10	5.7	N/A
58	5.8	1	1	10	5.8	N/A
59	5.9	1	1	10	5.9	N/A
60	6.0	1	1	10	6.0	N/A
61	6.1	1	1	10	6.1	N/A
62	6.2	1	1	10	6.2	N/A
63	6.3	1	1	10	6.3	N/A
64	6.4	1	1	10	6.4	N/A
65	6.5	1	1	10	6.5	N/A
66	6.6	1	1	10	6.6	N/A
67	6.7	1	1	10	6.7	N/A
68	6.8	1	1	10	6.8	N/A
69	6.9	1	1	10	6.9	N/A
70	7.0	1	1	10	7.0	N/A
71	7.1	1	1	10	7.1	N/A
72	7.2	1	1	10	7.2	N/A
73	7.3	1	1	10	7.3	N/A
74	7.4	1	1	10	7.4	N/A
75	7.5	1	1	10	7.5	N/A
76	7.6	1	1	10	7.6	N/A
77	7.7	1	1	10	7.7	N/A
78	7.8	1	1	10	7.8	N/A
79	7.9	1	1	10	7.9	N/A
80	8.0	2	2	20	4.0	4.0

Title: A phase 1b dose-finding study of DDFPe in acute ischemic stroke

PIs: [name] & [name]

Institution: UAMS

Sponsor: UAMS

Body Weight (kg)	DDFPe Dose 0.10mL/kg	Number of DDFPe 10mL Vials Required	Number of 10mL Syringes to be Prepared	Total Volume to be Prepared (mL)	Volume to be Administered from 1st syringe (mL)	Volume to be Administered from 2nd Syringe (mL)
81	8.1	2	2	20	4.1	4.0
82	8.2	2	2	20	4.2	4.0
83	8.3	2	2	20	4.3	4.0
84	8.4	2	2	20	4.4	4.0
85	8.5	2	2	20	4.5	4.0
86	8.6	2	2	20	4.6	4.0
87	8.7	2	2	20	4.7	4.0
88	8.8	2	2	20	4.8	4.0
89	8.9	2	2	20	4.9	4.0
90	9.0	2	2	20	5.0	4.0
91	9.1	2	2	20	5.1	4.0
92	9.2	2	2	20	5.2	4.0
93	9.3	2	2	20	5.3	4.0
94	9.4	2	2	20	5.4	4.0
95	9.5	2	2	20	5.5	4.0
96	9.6	2	2	20	5.6	4.0
97	9.7	2	2	20	5.7	4.0
98	9.8	2	2	20	5.8	4.0
99	9.9	2	2	20	5.9	4.0
100**	10.0	2	2	20	5.0	5.0

Total DDFPe Dose = 0.10 mL/kg x weight in kg.

*Minimum subject weight = 45 kg.

**Maximum subject weight used for dose calculation = 100 kg. For subjects weighing more than 100 kg, dose will be calculated based on a weight of 100 kg.

Title: A phase 1b dose-finding study of DDFPe in acute ischemic stroke

PIs: [name] & [name]

Institution: UAMS

Sponsor: UAMS

DDFPe dosage volume in cc for **0.17 mL/kg** based on patient body weight in kilograms (kg).

Body Weight (kg)	DDFPe Dose 0.17mL/kg (mL)	Number of DDFPe 10mL Vials Required	Number of 10mL Syringes	Total Volume to be Prepared (mL)	Volume to be Administered from 1st syringe (mL)	Volume to be Administered from 2nd syringe (mL)	Volume to be Administered from 3rd syringe (mL)
45*	7.6	1	1	10	7.6	N/A	N/A
46	7.8	1	1	10	7.8	N/A	N/A
47	8.0	1	1	10	8.0	N/A	N/A
48	8.2	1	1	10	8.2	N/A	N/A
49	8.3	1	1	10	8.3	N/A	N/A
50	8.5	1	1	10	8.5	N/A	N/A
51	8.7	1	1	10	8.7	N/A	N/A
52	8.8	1	1	10	8.8	N/A	N/A
53	9.0	2	2	20	4.5	4.5	N/A
54	9.2	2	2	20	4.6	4.6	N/A
55	9.4	2	2	20	4.7	4.7	N/A
56	9.5	2	2	20	4.8	4.7	N/A
57	9.7	2	2	20	4.9	4.8	N/A
58	9.9	2	2	20	5.0	4.9	N/A
59	10.0	2	2	20	5.0	5.0	N/A
60	10.2	2	2	20	5.1	5.1	N/A
61	10.4	2	2	20	5.2	5.2	N/A
62	10.5	2	2	20	5.3	5.2	N/A
63	10.7	2	2	20	5.4	5.3	N/A
64	10.9	2	2	20	5.5	5.4	N/A
65	11.0	2	2	20	5.5	5.5	N/A
66	11.2	2	2	20	5.6	5.6	N/A
67	11.4	2	2	20	5.7	5.7	N/A
68	11.6	2	2	20	5.8	5.8	N/A
69	11.7	2	2	20	5.9	5.8	N/A
70	11.9	2	2	20	6.0	5.9	N/A
71	12.1	2	2	20	6.1	6.0	N/A
72	12.2	2	2	20	6.1	6.1	N/A
73	12.4	2	2	20	6.2	6.2	N/A
74	12.6	2	2	20	6.3	6.3	N/A
75	12.8	2	2	20	6.4	6.4	N/A
76	12.9	2	2	20	6.5	6.4	N/A
77	13.1	2	2	20	6.6	6.5	N/A
78	13.3	2	2	20	6.7	6.6	N/A
79	13.4	2	2	20	6.7	6.7	N/A
80	13.6	2	2	20	6.8	6.8	N/A

Title: A phase 1b dose-finding study of DDFPe in acute ischemic stroke

PIs: [name] & [name]

Institution: UAMS

Sponsor: UAMS

Body Weight (kg)	DDFPe Dose 0.17mL/kg (mL)	Number of DDFPe 10mL Vials Required	Number of 10mL Syringes	Total Volume to be Prepared (mL)	Volume to be Administered from 1st syringe (mL)	Volume to be Administered from 2nd syringe (mL)	Volume to be Administered from 3rd syringe (mL)
81	13.8	2	2	20	6.9	6.9	N/A
82	13.9	2	2	20	7.0	6.9	N/A
83	14.1	2	2	20	7.1	7.0	N/A
84	14.3	2	2	20	7.2	7.1	N/A
85	14.4	2	2	20	7.2	7.2	N/A
86	14.6	2	2	20	7.3	7.3	N/A
87	14.8	2	2	20	7.4	7.4	N/A
88	15.0	2	2	20	7.5	7.5	N/A
89	15.1	2	2	20	7.6	7.5	N/A
90	15.3	2	2	20	7.7	7.6	N/A
91	15.5	2	2	20	7.8	7.7	N/A
92	15.6	2	2	20	7.8	7.8	N/A
93	15.8	2	2	20	7.9	7.9	N/A
94	16.0	2	2	20	8.0	8.0	N/A
95	16.2	3	3	30	6.0	6.0	4.2
96	16.3	3	3	30	6.0	6.0	4.3
97	16.5	3	3	30	6.0	6.0	4.5
98	16.7	3	3	30	6.0	6.0	4.7
99	16.8	3	3	30	6.0	6.0	4.8
100**	17.0	3	3	30	6.0	6.0	5.0

Total DDFPe Dose = 0.17 mL/kg x weight in kg.

*Minimum subject weight = 45 kg.

**Maximum subject weight used for dose calculation = 100 kg. For subjects weighing more than 100 kg, dose will be calculated based on a weight of 100 kg.

Title: A phase 1b dose-finding study of DDFPe in acute ischemic stroke
PIs: [name] & [name]
Institution: UAMS
Sponsor: UAMS

Appendix 3: Modified Rankin Scale

Subject Name: _____
Rate Name: _____
Date: _____

Scale to be administered as part of the exclusion criteria and again at follow up (discharge and end of study)

SCORE	DESCRIPTION
0	No symptoms at all
1	No significant disability despite symptoms; able to carry out all usual duties and activities
2	Slight disability; unable to carry out all previous activities, but able to look after own affairs without assistance
3	Moderate disability; requiring some help, but able to walk without assistance
4	Moderately severe disability: unable to walk without assistance and unable to attend to own bodily needs without assistance
5	Severe disability; bedridden, incontinent and requiring constant nursing attention
6	Dead

Score (0-6): _____

References

Rankin J. Cerebral vascular accidents in patients over the age of 60. Scot Med J 1957;2:200-215.

Title: A phase 1b dose-finding study of DDFPe in acute ischemic stroke

PIs: [name] & [name]

Institution: UAMS

Sponsor: UAMS

Appendix 4: Schedule of Time and Events

	Day 1					Day 4	Day 7±1 or Day of Discharge	Day 30 ±7	Day 90 ±14
Study Procedures	Screening (Baseline)	Dose #1 ^a	Dose #2 ^a	Dose #3 ^a	Post- Dose #3 ^b				
Informed Consent	X								
I/E Criteria	X								
Concomitant Meds	X	X	X	X	X				
Medical History ^c	X						X	X	X
Physical Exam ^c	X				X		X	X	
Weight	X								
Vital Signs ^d	X	X	X	X	X		X	X	
Pulse Oximetry ^e	X	X	X	X	X		X		
Modified Rankin Scale	X						X	X	X
NIHSS	X		X ^f	X ^f	X		X	X	
ECG ^g	X				X		X		
Pregnancy Test ^h	X								
Lab Studies ⁱ	X				X		X		
Administer DDFPe ^j		X	X	X					
Adverse Events		X	X	X	X	X	X	X	X

a Each dose of DDFPe or placebo is to be administered intravenously over 5-10 minutes. Start and stop times will be recorded as will the volume infused.

b Post-dose #3 concludes approximately 4-6 hours after the end of the Dose #3 infusion.

c Brief, targeted medical history and physical exam.

d Vital signs (blood pressure, heart rate, respiratory rate) will be done every 15 minutes through the end of Post-Dose #3 (approximately 4-6 hours) and then consistent with standard procedures for the hospital unit. Temperature will be done every 1-4 hours consistent with the hospital unit standard procedures.

e Continuous or spot readings may be taken; if continuous readings are used, record the measurement every 15 minutes.

f To be performed within 60 minutes following the dose.

g 12-lead ECG to be examined at the bedside by the study personnel and later reviewed by a board certified cardiologist.

h Serum pregnancy test will be done in pre-menopausal women.

i To include: CBC, electrolytes (Na, K, Cl), BUN, creatinine, LFTs, calcium, albumin, glucose

j DDFPe or placebo to be administered over 5-10 minutes intravenously through a peripheral or central IV. The interval between the end of one dose and the beginning of the next should be 90 ± 10 minutes.

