Study Product, Dose, Route, Regimen	Dodecafluoropentane emulsion (DDFPe) Dose Range: 0.05, 0.10, and 0.17 mL/kg (Maximum dose: 17 mL/dose) Route: Intravenous over 5-10 minutes every 90 ± 10 minutes x 3 doses Placebo - Intralipid® 20% IV fat emulsion Dose: Sterile 1:101 dilution of Intralipid® in aqueous sodium chloride (0.9% w/v) Route: Intravenous over 5-10 minutes every 90 ± 10 minutes x 3 doses
Duration of Administration	Approximately 3-4 hours
Reference Therapy	None
Primary Outcome Measures	DLT (dose limiting adverse events) including clinically significant changes in vital signs, peripheral oxygen saturation (pulse oximetry), clinical symptoms, NIH Stroke Scale, laboratory values, and ECG measurements, Grade 3 or higher scores on selected CTCAE 4 measures

Title: A phase 1b dose-finding study of DDFPe in acute ischemic stroke

PIs: [name] & [name]

Institution: UAMS

Sponsor: UAMS

ABBREVIATIONS

AE	Adverse Event
AIS	Acute ischemic stroke
ALT	Alanine Aminotransferase
ANOVA	Analysis of Variance
aPTT	Activated Partial Thromboplastin Time
AST	Aspartate Aminotransferase
AUC	Area under the Concentration vs. Time Curve
BP	Blood Pressure
BUN	Blood Urea Nitrogen
CL	Clearance
Cmax	Maximum Concentration
COPD	Chronic Obstructive Pulmonary Disease
CRF	Case Report Form
CT	Computed (Computerized) Tomography
CTCAE	Common Terminology Criteria for Adverse Events
DDFP	Dodecafluoropentane
DDFPe	Dodecafluoropentane emulsion
DBP	Diastolic Blood Pressure
DLT	Dose Limiting Toxicity
DSM	Data Safety Monitor
ECG	Electrocardiogram
FDA	Food and Drug Administration
HIPAA	Health Insurance Portability and Accountability Act
HR	Heart rate
IEC	Independent Ethics Committee
INR	International Normalized Ratio
IRB	Institutional Review Board
IV	Intravenous
LAR	Legally Authorized Representative
LFT	Liver Function Tests
mmHg	Millimeters of Mercury
mRS	modified Rankin Scale
mSec	Millisecond
MTD	Maximum Tolerated Dose
N/A	Not Applicable
ND	Not Done
NIH	National Institutes of Health
NIHSS	National Institutes of Health Stroke Scale
NSAID	Non-Steroidal Anti-Inflammatory Drug
NYHA	New York Heart Association
OTs	Oxygen Transporters
PHI	Personal Health Information
PTB	PE-Telomer-B
RR	Respiratory Rate

Title: A phase 1b dose-finding study of DDFPe in acute ischemic stroke

PIs: [name] & [name]

Institution: UAMS

Sponsor: UAMS

SAE	Serious Adverse Event
SBP	Systolic Blood Pressure
SD	Standard Deviation
Tmax	Time at Which the Maximum Concentration (Cmax) Occurs
tPA	Tissue Plasminogen Activator

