1.2 Brief Description of the Investigational Product

DDFPe is an emulsion of 2% dodecafluoropentane in stabilizers (sucrose, PE-Telomer B) and phosphate buffered saline (pH 7.0). Compared to higher molecular weight liquid fluorocarbons that have already been studied extensively as OTs, DDFPe carries far more oxygen per gram of fluorocarbon.

Stoichiometrically, DDFP has 200 times the oxygen carrying capacity compared to human hemoglobin. Consequently, if it were administered intravenously (IV) and passed through the lungs of patients breathing high concentrations of oxygen, it would take up large amounts of oxygen and increase the oxygen concentration in blood in a dose-dependent way. Hypothetically, by shifting ischemic environments to normal tissue pO₂ environments patient recovery from stroke will be improved.

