5.3.2 Dose Limiting Toxicity

Dose limiting toxicity (DLT) will be defined by the following criteria:

- Clinically significant changes in vital signs:
 - Heart rate \pm 50% from baseline
 - Respiratory rate >30 /min
 - Systolic blood pressure < 90 mmHg or >220 mmHg
 - Diastolic blood pressure >110 mmHg
- New (i.e. not seen at baseline) ECG changes consistent with:
 - Acute right ventricular dilation or strain
 - Incomplete or complete bundle branch block
 - Q waves in leads III and aVF
 - T-wave inversion and/or ST segment changes in the precordial leads
 - Any other clinically significant cardiac arrhythmia
- Common Terminology Criteria for Adverse Events (CTCAE) 4 Grade 3 or higher cough, dyspnea, chest pain-cardiac or non-cardiac, chest wall pain or hypoxia (See [Appendix 1](#) for specific criteria)
- NIHSS: sudden worsening of 4 or more from the baseline (pre-DDFPe initiation)
- The Medical Monitor will review all data collected at Post-Dose #3 (approximately 4-6 hours after the end of the Dose #3 infusion of DDFPe or placebo for each subject). Enrollment will be on hold until the Medical Monitor has reviewed the data and approves enrollment of an additional subject. The Medical Monitor may choose to temporarily halt the study if serious concerns arise regarding subject safety.

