7.1 Usual Care Provided by Treating Physician

Customary (routine) care for patients suffering a stroke will be offered as would be the case had the patient not enrolled in the trial. This may include physiological monitoring, medical procedures, drug therapy (including tPA), respiratory support, and ancillary or accessory care. Routine care will be directed by the patient's treating physician. If the treating physician believes that it is no longer in the best interest for the patient to continue in the study, he/she will contact the investigator and immediately stop all study-related procedures.

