7.6 Day 1: Study Procedures

After documentation that the subject passed the screening procedures and meets all Inclusion and Exclusion criteria, study personnel will check to assure that a patent intravenous catheter is in place for infusion of the DDFPe. The catheter should be used solely for infusion of DDFPe and compatible intravenous fluids during the study intervention period (from the initiation of Dose #1 to after the Dose #3 infusion is complete).

Dose #1: DDFPe will be ordered from the pharmacy and prepared as previously described. The time that the infusion begins will be recorded. The drug or placebo will be infused over 5-10 minutes. At the end of the infusion, the time will again be recorded. Vital signs and pulse oximetry will be monitored. Measurements will be recorded every 15 minutes. The subject will be observed for any signs of adverse events for 90 minutes after the completion of the infusion.

Dose # 2: Any new concomitant medications will be recorded. The second dose of DDFPe or placebo will be administered as previously described over 5-10 minutes. Times will be recorded at the beginning and end of the infusion as before. Vital signs and pulse oximetry will be monitored. Measurements will be recorded every 15 minutes. The NIHSS will be repeated within 60 minutes after the end of the DDFPe infusion. The subject will be observed for any signs of adverse events for 90 minutes after the completion of the infusion.

Dose #3: Any new concomitant medications will be recorded. The third dose of DDFPe or placebo will be administered as previously described over 5-10 minutes. Times will be recorded at the beginning and end of the infusion as before. Vital signs and pulse oximetry will be monitored. Measurements will be recorded every 15 minutes. The NIHSS will be repeated within 60 minutes after the end of the DDFPe

infusion. The subject will be observed for any signs of adverse events for 90 minutes after the completion of the infusion.

Vitals should be taken at all scheduled time points (i.e. every 15 minutes); however, deviations from scheduled times will not be considered protocol deviations. The exact date and time of each measurement will be recorded on the CRF.

Post-Dose #3: Approximately 4 ± 1 hours after the end of Dose #3, the following observations will be made:

- Concomitant medications administered after Dose #3
- A brief physical examination
- Vital signs (BP, HR, RR)
- Pulse oximeter measurement
- NIHSS
- ECG

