10.2 Clinical Data

Demographic data will be presented as the mean \pm SD (range) for normally distributed data (median \pm interquartile range for non-normal data).

Clinical data includes vital signs and pulse oximetry (pre- and post-intervention). Pre- and post-intervention data will be grouped and examined for differences using a two-sided t-test or ANOVA, as appropriate. Pre- and post- laboratory data will be compared in a similar manner. ECGs will be read by a board-certified cardiologist and clinically significant changes will be described.

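### Oxygen status is not required alongside pulse oximetry, so oxygen started or increased after baseline can obscure a fall in saturation

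*Combined protocol and SAP*

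**What the plan says.** Saturation is used in three places.

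- **Primary outcome.** The Study Summary lists "DLT (dose limiting adverse events) including clinically significant changes in vital signs, peripheral oxygen saturation (pulse oximetry), clinical symptoms, NIH Stroke Scale" among the primary outcome measures.
- **DLT.** Section 5.3.2 counts "Common Terminology Criteria for Adverse Events (CTCAE) 4 Grade 3 or higher cough, dyspnea, chest pain-cardiac or non-cardiac, chest wall pain or hypoxia". Appendix 1 describes Grade 3 hypoxia as "Decreased oxygen saturation at rest (e.g., pulse oximeter <88% or PaO2 <=55 mm Hg". It attaches no condition about inspired oxygen. Section 5.3.2 gives saturation no threshold of its own, so it enters the DLT only through this grade.
- **Analysis.** Section 10.2 states: "Clinical data includes vital signs and pulse oximetry (pre- and post-intervention". The pre and post values are to be compared by a two-sided t-test or ANOVA. No covariate or stratum for oxygen is named.

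On measurement, Section 7.6 says after each dose: "Vital signs and pulse oximetry will be monitored. Measurements will be recorded every 15 minutes". Appendix 4 footnote e adds "Continuous or spot readings may be taken; if continuous readings are used, record the measurement every 15 minutes". Neither mentions what the subject is breathing.

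On oxygen itself, Section 7.1 allows "drug therapy (including tPA), respiratory support, and ancillary or accessory care" at the treating physician's direction, and Section 8.7 says that taking part leads to no standard treatment being withheld. The nearest recording item is concomitant medication (Section 7.5.5 and Appendix 4), which does not name oxygen.

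**The concern.** A saturation value depends on the oxygen being breathed. The same reading on room air and on supplemental oxygen describes two different states of the lungs, and the protocol asks for nothing that would tell them apart. Section 8.6 lists reversible inflammatory lung changes among the risks, so respiratory effects are ones this trial should be able to see.

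Two uses of the data are exposed. In the pre/post comparison, oxygen started or increased between the two readings pulls the post value up and can cancel a real fall. In the DLT assessment, oxygen given early enough can hold a subject above the Grade 3 example value. With only six DDFPe subjects per cohort and a limit of three with a DLT (Section 5.3.3), one subject classified differently can matter.

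**Working it through.** The plan states no figure on this point, and Section 10.1 says that no sample size estimate was made, so there is nothing to reproduce. The check has three parts.

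**1. When would the hypoxia DLT be missed?** Reading Section 5.3.2 against Appendix 1, all of the following must hold:

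- oxygen is started or increased before a resting saturation below 88% is recorded, because a lower value recorded first already fits Grade 3;
- respiratory rate stays at or below 30/min, since a higher rate is a separate DLT;
- there is no Grade 3 dyspnea, which includes breathlessness at rest;
- there is no Grade 4 hypoxia, which Appendix 1 defines by airway compromise and urgent intervention;
- the assessor treats 88% as a fixed limit, although Appendix 1 offers it as an example.

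Grade 2 mentions intermittent supplemental oxygen but is not a DLT. The gap is real and narrow.

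**2. Effect on the pre/post mean.** Let D be the true mean fall, f the fraction of subjects with new or increased oxygen after baseline, and g the gain in points that each of them has from it. The observed fall is D − f × g. The documents give none of these values; all are assumed.

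| D | f | g | Observed fall |
|---|---|---|---|
| 2 | 0.25 | 4 | 2 − 0.25 × 4 = 1 |
| 2 | 0.50 | 2 | 2 − 0.50 × 2 = 1 |
| 2 | 0.50 | 4 | 2 − 0.50 × 4 = 0 |
| 2 | 0.75 | 4 | 2 − 0.75 × 4 = −1 (an apparent rise) |
| 3 | 0.50 | 4 | 3 − 0.50 × 4 = 1 |

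Oxygen that is unchanged between the two readings does not enter f. A reduction in oxygen would act in the opposite direction.

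**3. Possible effect on the escalation rule.** Section 5.3.3 declares the MTD exceeded when three or more DDFPe subjects in a cohort have a DLT; Section 3.1 gives six DDFPe subjects per cohort. With per-subject DLT probability p,

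P(3 or more of 6) = 1 − Σ (k = 0 to 2) C(6,k) p^k (1−p)^(6−k).

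Let h be the true probability of a hypoxia DLT, o that of any other DLT (taken as independent), and m the share of hypoxia DLTs masked. Then p = 1 − (1 − o)(1 − h(1 − m)). Again all three are assumed.

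| h | o | p, m = 0 | P, m = 0 | p, m = 0.5 | P, m = 0.5 |
|---|---|---|---|---|---|
| 0.2 | 0 | 0.20 | 0.099 | 0.10 | 0.016 |
| 0.4 | 0 | 0.40 | 0.456 | 0.20 | 0.099 |
| 0.2 | 0.10 | 0.28 | 0.220 | 0.19 | 0.087 |
| 0.4 | 0.10 | 0.46 | 0.579 | 0.28 | 0.220 |

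For the first entry with h = 0.4: 1 − (0.0467 + 0.1866 + 0.3110) = 0.456. The table shows how sensitive a limit of three in six would be if masking were common. It is no estimate for this trial, and part 1 gives reason to expect that m is well below one half.

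**The case against.** The strongest reply is that the protocol has other ways to see the event. Section 8.1 makes an abnormal diagnostic result an adverse event if it leads to additional treatment, and a desaturation treated with new oxygen fits that. Section 8.2 requires every adverse event to be recorded. The Medical Monitor reviews each subject's data before the next is enrolled and may halt the study (Sections 5.3.2, 5.3.3, 8.4 and 8.5). Section 6.4 lists a significant change in oxygenation as a reason to discontinue the product. Exclusions 6.3.10 and 6.3.11 remove uncontrolled or oxygen-requiring lung disease and acute respiratory disease. All of this stands, and it makes it unlikely that a treated desaturation would pass unseen. It does not put oxygen status beside the readings, and it does nothing for the comparison in Section 10.2.

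Four stronger readings are tempting, and the documents do not support them.

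- *The primary outcome is biased towards tolerability.* The MTD follows the DLT count in Section 5.3.3. The pre/post test in Section 10.2 does not feed it, so confounding there is not by itself bias in the primary outcome.
- *The information cannot be recovered.* The case report form is not among the documents, and Section 9.4 counts hospital records as source documents. What can be said is that the protocol does not require oxygen status to be recorded.
- *Trial subjects receive high-concentration oxygen.* Section 1.2 speaks of the drug having "passed through the lungs of patients breathing high concentrations of oxygen", but as a hypothetical account of its mechanism, not a description of care in this trial.
- *A number of affected readings or subjects can be stated.* The 4–6 hour duration in Appendix 4 is in footnote d, for blood pressure, heart rate and respiratory rate. Footnote e gives none for oximetry, and no rate of oxygen use appears anywhere.

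Placebo subjects share the same usual care, which helps in principle. But there are two per cohort, six in all (3 × 2), and Section 10.2 specifies no between-arm comparison of saturation.

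**Conclusion.** The point holds in limited form. Followed as written, the plan can produce a pre/post saturation result that understates a fall, or shows none, whenever oxygen is started or increased after baseline. That part follows directly from Sections 7.1, 7.6 and 10.2 and Appendix 4; only its size depends on assumed rates and gains.

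Masking of a hypoxia DLT is possible only under the joint conditions set out in the check, and the event would probably still reach the Medical Monitor as an adverse event. The effect on the MTD decision is therefore possible, of unknown size, and not shown to be large. This is a worthwhile and inexpensive improvement to data collection and reporting. It does not show that the dose-escalation design fails.

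**What to change.** - **Section 7.6 and Appendix 4 footnote e:** record oxygen device and flow (or room air/FiO2) at baseline and with each recorded saturation.
- **Medical Monitor review (Sections 5.3.2 and 8.5):** include oxygen status in the data already reviewed after each subject. The DLT criteria and the 88% example value stay as they are, and no rule for giving oxygen is implied.
- **Section 10.2:** report saturation by oxygen status, with the number of subjects in each arm who had new or increased oxygen since baseline.

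The cost is one extra entry per recorded saturation, made by the same staff at the same time, and one line in the safety tables. The only downside is slightly more transcription.
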